### Non-Clinically Significant (NCS) Laboratory Abnormalities

All laboratory results must be filed in the patient's medical record and be monitored. The investigator must review laboratory results in a timely manner demonstrated by signature/date and assignment of clinical significance assessment. Non-clinically-significant laboratory abnormalities, i.e., minor deviations from the normal range, are expected and it is likely that no medical intervention will be required. Such results will not be considered to be AEs.

# **Clinically Significant (CS) Laboratory Abnormalities**

Any laboratory abnormality that is considered to be clinically significant by the investigator will be recorded on the AE eCRF. A clinically significant abnormal test result will be considered an AE if:

• It is not associated with an already reported AE, diagnosis or pre-existing condition

- There is a change in concomitant medication or intervention as needed, in direct response to the laboratory result
- The investigator exercises his/her discretion to make significance determinations for any patient laboratory result or result that requires intervention

All such lab abnormalities will be repeated and assessed by the investigator, or licensed (MD), as soon as possible for "seriousness" and if they meet the regulatory definition of "serious", they will be reported as SAEs following regulatory and protocol requirements. Repeat laboratory tests may be run in order to monitor the result.

### Serious Laboratory Abnormalities

Any lab abnormality meeting the regulatory definition of "serious" must be recorded on both the AE eCRF/record and the SAE Form. If a patient experiences a serious toxicity or dies, the FDA will be notified within 24 hours, as required.

### 11.3.10. Pregnancy

If any patient becomes pregnant following the first dose of tesevatinib, the patient will be taken off study and followed regularly until birth or termination of the pregnancy. The pregnancy must be immediately reported to the sponsor. Forms for reporting pregnancies will be provided to the study sites upon request. The anticipated date of birth or termination of the pregnancy should be provided at the time of the initial report. The outcome of a pregnancy must be reported to the Medical Monitor as soon as it is known. If the pregnancy ends for any reason before the anticipated date initially reported, the investigator must notify the Kadmon Medical Monitor as soon as possible.

If the outcome of the pregnancy meets any criterion for classification as a SAE (including stillbirth, neonatal death, spontaneous abortion, or congenital anomaly – including that in an aborted fetus) the investigator must follow the procedures for reporting SAEs. Any neonatal death occurring  $\leq$  30 days after birth will be reported as a SAE.

# 11.3.11. Serious Adverse Event Reporting

### **11.3.11.1.** Governing Regulatory Requirements

Compliance with this request for prompt reporting is essential in that the sponsor is responsible for informing the US Food and Drug Administration (FDA) as well as all other participating investigators of the event.

Under FDA ruling (US Code of Federal Regulations, Title 21 CFR Part 312.32) and the Guidance for Industry and Investigators Safety Reporting Requirements for INDs and BA/BE Studies, the sponsor is required to submit written documentation, in the form of an IND safety report, detailing:

• Any event associated with the use of the drug, that is both serious and unexpected, or

• Any findings from clinical, epidemiological, or pooled analysis of multiple studies or any findings from animal or in vitro testing that suggest a significant risk in humans exposed to the drug.

Written submission must be made by the sponsor to the FDA and the IRBs as soon as possible and in no event later than 15 calendar days after the sponsor's initial notification of the event. Any unexpected fatal or life-threatening suspected adverse reaction must be reported to FDA no later than 7 calendar days after the sponsor's initial receipt of the information. The sponsor shall also inform all investigators.

# 11.3.11.2. Time-Frame for Reporting

Any death, pregnancy, or SAE experienced by a patient from the time of informed consent until 30 days after receiving the last dose of study drug, regardless of relationship to study drug, or any death that occurs more than 30 days after receiving study drug, and is believed to be study drug-related, must be promptly reported (within 24 hours of the investigator becoming aware of the event) by fax to the sponsor (or designee). [contact].

In the event of an issue with the fax line, forward the SAE form via email to [contact].

The investigator will be able to contact the safety Medical Monitor at all times:

[name] Vice President Clinical Development Kadmon Corporation [name] Cambridge, MA 02142 [contact] E-mail: [contact]

### 11.3.11.3. Information to be Provided by the Investigator

SAEs must be recorded on the SAE eCRF page. This requirement includes all SAEs that occur after informed consent and through 30 days after last dose of study treatment, and in addition, any SAE that are assessed as possibly related to study treatment by the investigator, even if the SAE occurs more than 30 days after the last dose of study treatment.

The minimum information required for SAE reporting includes identity of investigator, site number, patient number, an event description, SAE term(s), onset date, the reason why the event is considered to be serious (i.e., the seriousness criteria) and the investigator's assessment of the relationship of the event to study treatment (not related, unlikely-related, possibly related, probably related, or definitely related). Additional SAE information including medications or other therapeutic measures used to treat the event, action taken with the study treatment due to the event, and the outcome/resolution of the event will be recorded on the SAE form. Forms for reporting SAEs will be provided to the study sites.

In all cases, the investigator should continue to monitor the clinical situation and report all material facts relating to the progression or outcome of the SAE. Furthermore, the investigator may be required to provide supplementary information as requested by the Kadmon Drug Safety personnel or designee.

When reporting SAEs, the following additional points should be noted:

- When the diagnosis of an SAE is known or suspected, the investigator should report the diagnosis or syndrome as the primary SAE term, rather than as signs or symptoms. Signs and symptoms may then be described in the event description. For example, dyspnea should not be used as an SAE term if the diagnosis which caused the dyspnea is known to be malignant pleural effusion. There is no requirement that the chosen SAE term be listed in the National Cancer Institute (NCI) Common Terminology Criteria for Adverse Events (CTCAE) Version 4.03.
- Death should not be reported as an SAE, but as an outcome of a specific SAE, unless the event preceding the death is unknown. In the exceptional case where the events leading to death are unknown, then death may be used as an event term. If an autopsy was performed, the autopsy report should be provided.
- While most hospitalizations necessitate reporting of an SAE, some hospitalizations do not require SAE reporting, as follows:
  - Elective or previously scheduled surgery, e.g. a previously scheduled ventral hernia repair
  - Procedures for pre-existing conditions that have not worsened after initiation of treatment
  - Pre-specified study hospitalizations for observation
  - Events that result in hospital stays of less than 24 hours and that do not require admission, e.g. an emergency room visit for hematuria that results in a diagnosis of cystitis and discharge to home on oral antibiotics
- SAEs must, however, be reported for any surgical or procedural complication resulting in prolongation of the hospitalization.

### 11.3.12. Regulatory Reporting

Kadmon Drug Safety (or designee) will process and evaluate all SAEs as soon as the reports are received. For each SAE received, Kadmon will make a determination as to whether the criteria for expedited reporting have been met.

Kadmon (or designee) will submit SAEs that meet the criteria for expedited reporting to the Regulatory Authorities in accordance with local regulations governing safety reporting. Reporting of SAEs by the investigator to his or her IRB will be done in accordance with the standard operating procedures and policies of the IRB. Adequate documentation must be maintained showing that the IRB was properly notified.

### 11.3.13. Follow-up Information on a Serious Adverse Event

Appropriate diagnostic tests should be performed and therapeutic measures, if indicated, should be instituted. Appropriate consultation and follow-up evaluations should be carried out until the event has returned to baseline or is otherwise explained by the investigator.

Follow-up data concerning the SAE (e.g., diagnostic test reports, physician's summaries, etc.) also must be submitted to Kadmon, as they become available, by telefax or email transmission, until resolution of the SAE.

# 11.4. Other Safety Considerations

# 11.4.1. Medication Errors

Any medication error that results in an AE, even if it does not meet the definition of serious, requires reporting within 24 hours to the Medical Monitor. An overdose of tesevatinib without any associated signs or symptoms, unless the patient is hospitalized for observation, will not constitute an AE but will be recorded as a protocol deviation.

# 11.4.2. Follow-Up of Serious Adverse Events

Any SAE that led to treatment discontinuation (including clinically significant abnormal laboratory values that meet these criteria) and is ongoing 30 days after last dose of study treatment must be followed until either resolution of the event or determination by the investigator that the event has returned to baseline/resolved, Grade 1 or has become stable. This follow-up guidance also applies to SAEs that occur *more than 30 days after last dose* of study treatment.

# 11.5. Safety Monitoring

Patients will be closely monitored for adverse events of interest and potential drug-drug interactions through standard safety reporting as well as a regular medical review of safety data outputs from both the clinical and pharmacovigilance databases. Particular attention will be paid to the success of diarrhea and rash management strategies and the use of concomitant medications which have a risk of drug-drug interaction or QTc prolongation. SAEs, including deaths, and withdrawals due to adverse events will also be closely monitored. A central laboratory will be used to monitor for QTc prolongation, and any study drug reintroduction in the case of QTc prolongation will only be performed with the agreement of the Medical Monitor.

A Data Monitoring Committee will not be used for this study.

# 12. STUDY ASSESSMENTS AND PROCEDURES

Informed consent must be obtained before any study-specific samples are taken or study-specific tests or evaluations are conducted. Screening assessments should be performed within 28 days before the first dose of study drug is administered on Day 1. Study eligibility will be based on satisfying all of the study inclusion and exclusion criteria for each cohort.

Study Day 1 is defined as the date the patient takes the first dose of study drug, with subsequent study days numbered sequentially thereafter.

If significant changes from baseline are noted during the course of the study, additional unscheduled clinic visits may be undertaken by the investigator, or requested by the sponsor, in order to determine both the relevance of the finding(s) and the duration of the event(s).

# 12.1. Procedures to be Performed

### 12.1.1. Informed Consent

All patients must take part in the informed consent process. Adequate time must be allowed for the patient to ask questions and make a voluntary decision. No protocol-specific procedures, including screening procedures that are not standard of care procedures, are to be performed until the patient has signed and dated an IRB/IEC-approved ICF.

# 12.1.2. Demographics and Medical History

A complete medical history will be taken. Medical history includes clinically significant diseases, surgeries, history of glioblastoma (including date of diagnosis, history of prior low-grade astrocytoma, location of disease, prior cancer therapies and procedures), and all medications (e.g., prescription drugs, over-the-counter drugs, herbal/homeopathic remedies, nutritional supplements) used by the patient within 28 days prior to randomization.

Demographic data will include age, sex, and self-reported race/ethnicity.

# 12.1.3. Complete and Abbreviated Physical Examinations

On days in which a complete physical examination is required, the investigator should perform a thorough examination of all body systems (exception: genitourinary and reproductive should be symptom-directed). On days in which a limited physical examination is required, the investigator should inquire about signs/symptoms, general appearance, eyes, heart and pulse, lungs, abdomen (liver/spleen), kidneys, and neurological (symptom directed only). Interval history should be recorded at all study visits.

# 12.1.4. Detailed Neurological Examination

Neurological exam should include full cranial nerve central and peripheral, motor and sensory assessments.

### 12.1.5. Vital Sign Measurements

Vital sign measurements will be collected after the patient has been sitting for 5 minutes. Vital sign assessments will include measurements of sitting blood pressure (mm Hg), heart rate (beats per minute), respiration rate (breaths per minute), and temperature (Celsius/Fahrenheit).

Please note that blood pressure measurements are to be performed using the appropriate technique (per guidelines of the American Heart Association). Specifically, patients should be seated quietly for at least 5 minutes in a chair with their backs supported, their feet flat on floor (legs uncrossed), and their arms bared on a hard surface, with the arm slightly abducted and bent, with palm up and the midpoint of upper arm at heart level. Correct cuff and bladder size should be utilized. Record cuff size, arm used, and patient's position (if not seated).

### 12.1.6. Hematology and Serum Chemistries.

Samples for laboratory assessments (hematology and serum chemistries) are to be collected. A Local laboratory will perform hematology and serum chemistry tests and results will be provided to the investigator. Blood and urine samples for hematology, serum chemistry will be prepared using standard procedures. Laboratory panels are defined as listed in
Timepoint (Study Day)	Cycle 26 Day 1 (± 3d)	Cycle 28 Day 1 (± 3d)	Cycle 30 Day 1 (± 3d)	Cycle 32 Day 1 (± 3d)	Cycle 34 Day 1 (± 3d)	Cycle 36+ Day 1 (± 3d)	EOS Tx i	30-Day FU j (± 5d)	UNS k
Physical Examination a	Х	X	Х	Х	Х	Х	Х	Х	Х
Neurological Examination b	Х	X	Х	Х	X	Х			X
Vital Signs c	Х	X	Х	Х	X	Х	Х	Х	X
Safety Labs d	Х	X	Х	Х	X	Х	Х	Х	X
12-Lead ECG e	X	X	Х	Х	X	X	Х		X
Disease Assessment f	Х	X	Х	Х	X	Х	Х		X
Karnofsky performance status	X	X	X	Х	X	X	Х		X
Corticosteroid use	X	X	Х	Х	X	X	Х		X
MRI tumor assessment	Х	X	Х	Х	X	X	Х		X
Concomitant Medications	Х	X	Х	Х	Х	Х	Х	Х	Х
Tesevatinib Dispensing g	X	Х	Х	Х	X	Х			X
AE Monitoringh	X	X	X	Х	X	X	Х		Х

Table 2b:Schedule of Study Assessments for Subjects Completing 24 Cycles of TesevatinibTreatment

d = day; ECG = electrocardiogram; EOS = end of study; FU = follow-up; KPS = Karnofsky Performance Status; LTFU = long-term follow-up; MRI = magnetic resonance imaging; PK = pharmacokinetic; UNS = unscheduled; Tx = treatment

w: Abbreviated PE is acceptable (to be completed in a targeted manner covering related body systems).

x: Neurological exam should include full cranial nerve central and peripheral, motor and sensory assessments.

y: Vital sign measurements (blood pressure, heart rate, respiratory rate, and temperature) to be obtained with patient in sitting position.

z: To be drawn and analyzed locally. Safety labs = hematology and clinical chemistry. See Table 2b.

aa: Supine 12-Lead ECGs will be performed at each visit.

bb: The assessment should be performed every 8 weeks. Radiological assessment must be performed with a brain MRI scan and should be consistent throughout all visits.

cc: Study drug should be dispensed and accounted for from previous visit.

dd: AEs are to be collected from the time of informed consent through 30 days after last dose of study drug.

ee: The End-of-Study Drug Treatment visit is to occur as soon as possible after the patient's last dose of study drug. This may occur at the visit at which disease progression is diagnosed. Tumor assessment does not need to be performed if it was performed in the previous 8 weeks.

ff: The 30-Day Follow-Up visit should occur 30 days (±5 days) after the patients' last dose of tesevatinib, but prior to starting on a new therapy. This may occur prior to 30 days if the new therapy is started within 30 days of last dose of study drug. Assessments for the 30-day follow up may be done by telephone.

gg: For unscheduled visits, study assessments are at the investigator's discretion.

Table 3. In addition to central laboratory testing, a local laboratory will perform serum chemistry tests on Day 15 of each cycle from Cycle 2 through Cycle 6 for additional safety data. The local laboratory will perform all the serum chemistry tests included in Table 2 with the exception of Cystatin C.

Subjects who have completed 24 cycles of treatment without disease progression or unacceptable toxicity will have safety laboratory assessments collected at each bi-monthly visit. The local laboratory will perform hematology and serum chemistry tests. Laboratory panels are defined as listed in Table 2b.

Abnormalities in clinical laboratory tests that lead to a change in patient management (e.g. dose delay, requirement for additional medication or monitoring) are considered clinically significant for the purposes of this study, and will be recorded on the AE electronic case report form (eCRF) page. If laboratory values constitute part of an event that meets criteria defining it as serious, the event (and associated lab values) must be reported as an SAE (see Section 11.3).

#### 12.1.7. Pregnancy Test

Urine pregnancy tests are to be performed for females of childbearing potential. Positive urine tests are to be confirmed by a serum test.

## 12.1.9. 12-Lead Electrocardiogram (ECG)

Supine 12-Lead ECGs will be performed at screening; predose, and once within 4 - 8 hours postdose on Days 1 and 15 of Cycle 1; pre-dose on Day 1 of Cycles 2 and beyond; and at the End of Study Drug Treatment visit. ECGs will be read by a central laboratory.

ECGs are to be performed before any blood sample collection when possible.

ECGs are to be repeated three times consecutively within 30 minutes (must have an interval of at least 1–2 minutes between ECGs).

During the study, all ECGs will be digitally analyzed by a validated central ECG laboratory vendor. This central vendor will place ECG machines at sites under contract with Kadmon. ECGs will be transmitted electronically to the central vendor for analysis. Reports, including clinical alerts resulting from the analysis of the ECGs, will be provided back to sites. Sites will be trained on the use of the ECG machines, and instructions for performing ECG assessments will be provided in the ECG manual. Although ECGs will be read by a central laboratory, sites should take action if clinically significant abnormalities are detected at time of ECG.

Subjects who have completed 24 cycles of treatment without disease progression or unacceptable toxicity will have ECG assessments performed at each bi-monthly visit. These ECG assessments will be performed locally and read by qualified site personnel.

Prior to enrollment, all patients must demonstrate an average screening QTc(F) value of  $\leq 470$  msec by central digital analysis. Immediate clinical management of patients will initially be based on results of machine-read ECGs at the sites. However, the central digital analysis will prevail as it becomes available. In addition, the central digital analysis will be used for any AE and SAE documentation.

An increase in QTc(F) interval (by central digital analysis) to a value > 60 msec above baseline or to the level of  $\geq$  500 msec requires further monitoring. After discussion with the Medical Monitor (if  $\geq$  500 msec) on appropriate management, the patient may be removed from the trial (see guidelines in Section 9.1.4.3.1).

Abnormalities in the ECG that lead to a change in patient management (e.g., requirement for additional medication or monitoring) or result in clinical signs and symptoms are considered clinically significant for the purposes of this study and will be recorded on the AE eCRF. If ECG abnormalities meet criteria defining them as serious, they must be reported as SAE (see Section 11.3).

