- h: Supine 12-Lead ECGs will be performed at screening; predose, and once within the 4 8 hours postdose on Days 1 and 15 of Cycle 1; pre-dose on Day 1 of Cycles 2 and beyond; and at End of Study Drug Treatment visit. At each timepoint, repeat ECG three times consecutively within 30 minutes (must have an interval of at least 1–2 minutes between ECGs). ECGs will be read by a central laboratory. Following dose reduction and resumption of study drug treatment, ECGs must be repeated weekly for 2 weeks, then on Day 1 of each cycle following restart of study drug.
- The assessment is intended to be done prior to starting cycle 2, 3, 5, 7+ but should be performed every 8 weeks. Radiological assessment must be performed with a brain MRI scan. The method of radiological assessment should be consistent throughout all visits. Disease assessment during the screening period is to be performed within 7 days before study drug administration and must be used as the baseline radiological assessment. The corticosteroid dose should be kept stable for 5 days prior to the MRI scan. During the study, disease assessments should be performed at week 4 and 8 after the date of first study treatment and then every 8 weeks (at Week 16, 24, etc.), regardless of treatment delays. For patients who discontinue treatment for other reasons than PD, disease assessment in the follow-up period should continue every 8 weeks (according to the original schedule) until disease progression. For patients with PD, disease assessment at the EOS is only required if not performed within the previous 8 weeks.
- j: Patients will complete the questionnaire pre-dose on Day 1 of Cycles 1 and 2; every 8 weeks after study drug administration (i.e., coinciding with the schedule of disease assessments); and at the EOS. Patients who discontinue study treatment for reasons other than disease progression will also complete the questionnaire every 8 weeks during follow-up until the time of documented disease progression. Patients must complete the questionnaire prior to any other tests or assessments and prior to any discussion of the patient's progress with their physician or any other healthcare personnel at the site.
- k: Blood samples for tesevatinib plasma concentrations should be drawn prior to study drug administration.
- 1: Tesevatinib will be administered at the dose of 300 mg once daily. Study drug should be dispensed and accounted for from previous visit.

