### 9.1.4.3.1. Management of QTc(F) Interval Prolongation

The following guidelines should be used in the management of QTc(F) prolongation. Patients will have ECGs performed at times designated by the protocol (refer to Table 1).

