- Vital sign measurements (predose and 1 and 4 hours postdose) (sitting blood pressure, heart rate, respiratory rate, temperature)
- Limited physical examination
- Clinical laboratory tests (hematology, cystatin-C, serum chemistry panel and urinalysis)
- Supine 12-Lead ECG (to be performed predose, and 4 8 hours postdose prior to any blood sample collection) (repeat three times consecutively within 30 minutes [must have an interval of at least 1-2 minutes between ECGs])
- Tesevatinib administration
- Plasma sample predose for tesevatinib concentration

- Concomitant medications
- AE assessment

#### 12.2.4. Cycle 2; Day 1

At the Cycle 2, Day 1 visit ( $\pm$  3 days), the following procedures and evaluations will be performed:

- Vital sign measurements (sitting blood pressure, heart rate, respiratory rate, temperature)
- Complete physical examination
- Clinical laboratory tests (hematology, cystatin-C, serum chemistry panel and urinalysis)
- Urine pregnancy test, if applicable. Positive results are to be confirmed with serum testing.
- Supine 12-Lead ECG (to be performed predose, and 4 8 hours postdose prior to any blood sample collection) (repeat three times consecutively within 30 minutes [must have an interval of at least 1-2 minutes between ECGs])
- Completion of PRO MDASI-BT
- Disease assessment (MRI, clinical status, corticosteroid use and overall disease assessment)
- Tesevatinib administration
- Plasma sample predose for tesevatinib concentration
- Concomitant medications
- AE assessment
- Issue study drug diary
- Dispense study drug

#### 12.2.5. Cycle 3; Day 1

At the Cycle 3, Day 1 visit ( $\pm$  3 days), the following procedures and evaluations will be performed:

- Vital sign measurements (sitting blood pressure, heart rate, respiratory rate, temperature)
- Complete physical examination
- Clinical laboratory tests (hematology, cystatin-C, serum chemistry panel and urinalysis)

- Urine pregnancy test, if applicable. Positive results are to be confirmed with serum testing.
- Supine 12-Lead ECG (to be performed predose, and 4 8 hours postdose prior to any blood sample collection) (repeat three times consecutively within 30 minutes [must have an interval of at least 1-2 minutes between ECGs])
- Neurological examination
- Plasma sample predose for tesevatinib concentration
- Disease assessment (MRI, clinical status, corticosteroid use and overall disease assessment)
- Tesevatinib administration
- PRO MDASI-BT
- Concomitant medications

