## 12.2.12. End-of-Study Drug Treatment Visit (EOS)

As soon as possible after the last dose of study drug, patients are to return to the study site to complete all end-of-study drug treatment assessments as described below. This may occur at the visit at which disease progression is diagnosed.

• Vital sign measurements (sitting blood pressure, heart rate, respiratory rate, temperature)

- Complete physical examination
- Clinical laboratory tests (hematology, cystatin-C, serum chemistry panel and urinalysis)
- Urine pregnancy test, if applicable. Positive results are to be confirmed with serum testing.
- Supine 12-Lead ECG (to be performed predose, and 4 8 hours postdose prior to any blood sample collection) (repeat three times consecutively within 30 minutes [must have an interval of at least 1-2 minutes between ECGs])
- Disease assessment (MRI, clinical status, corticosteroid use and overall disease assessment) if not done within the previous 8 weeks. If PD was not observed prior to the EOS visit, disease assessments should be performed until PD.
- PRO MDASI-BT
- Concomitant medications
- AE assessment
- Collect study drug diary
- Collect study drug

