#### 3.10.1 Adverse Events

AEs will be coded using the MedDRA dictionary (Version 20.1 or higher). Treatment-emergent AEs (TEAEs) are any AE occurring or worsening in severity after the first administration of study medication. All AEs (including SAEs) will be graded using the 5-point Common Terminology Criteria for Adverse Events (CTCAE) V4.03 scale (mild, moderate, severe, life-threatening, or death). Causality with tesevatinib will be classified as: definitely related; probably related; possibly related; unlikely related; or not related.

The investigator will further assess the relationship of AEs to tesevatinib or the underlying disease.

The number and percentage of patients who experienced at least one TEAE as well as the number and percentage of patients who experienced AEs of each specific SOC and PT will be presented. For the presentation of AE incidences, the SOCs and the PTs within each SOC will be presented by decreasing total frequency. Tabulation by maximum severity and relationship to tesevatinib will also be included by treatment group.

The TEAEs, Grade  $\geq$  3 TEAEs, SAEs, and TEAEs leading to dose modification/discontinuation will be summarized by treatment arm, SOC, and PT. These analyses will be repeated for events considered related (definitely related/probably related/possibly related) to tesevatinib.

Subject listings will be provided for SAEs, AEs resulting in study drug discontinuation and deaths.

Adverse events will also be presented in listings. Time to onset and duration of AEs will be included in listings, along with action taken and outcome.

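### SAP QTcF category tables leave out unscheduled ECGs and have no rule for visits with both predose and postdose readings, so they can undercount patients' worst QTcF

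*Protocol*

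**What the plan says.** **SAP.** Section 3.10.4 plans descriptive ECG statistics at each time point that has triplicate ECGs. Its QTcF tables are laid out differently. They count patients by study visit in four value bands (up to 450, above 450 to 480, above 480 to 500, above 500 msec) and four change bands (up to 0, above 0 to 30, above 30 to 60, above 60 msec). No rule says which reading places a patient in a band. Section 3.10 restricts data from unscheduled visits to listings. Section 3.10.2 plans shifts to the worst post-baseline grade for laboratory values; 3.10.4 has no counterpart for QTcF.

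**Protocol, ECG schedule.** Section 12.1.9 and Table 1 footnote h agree. Predose and postdose ECGs are taken on Cycle 1 Days 1 and 15, and after that, in 12.1.9, "pre-dose on Day 1 of Cycles 2 and beyond; and at the End of Study Drug Treatment visit" and, in footnote h, "pre-dose on Day 1 of Cycles 2 and beyond; and at End of Study Drug Treatment visit". The visit lists in 12.2.4–12.2.9 (Day 1 of Cycles 2 to 24) instead each read "Supine 12-Lead ECG (to be performed predose, and 4 8 hours postdose prior to any blood sample collection" (the missing dash in the hour range comes from text extraction). The same bullet stands in 12.2.12, for a visit described thus: "As soon as possible after the last dose of study drug, patients are to return to the study site".

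**Protocol, other ECGs.** Section 9.1.4.3 calls for an ECG when symptoms suggest arrhythmia. Section 9.1.4.3.1 and Table 1 footnote h require weekly ECGs for two weeks when treatment resumes after a dose reduction.

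**The concern.** QTc prolongation is an adverse event of special interest (protocol 9.1.4), and protocol 5.2 reports that it increased with plasma concentration. The readings most likely to show it are postdose readings and ECGs taken because something prompted them. The QTcF tables do not say how the first are counted and leave out the second. A table by visit also has no row for the number of patients who ever crossed a limit: a patient above 480 msec at two visits appears twice, and one above it only between visits does not appear at all. At stake is whether the QTcF summary in the study report shows the drug's worst observed effect in each patient.

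**Working it through.** The plan gives no figure to reproduce here, so the check compares the texts, with a little arithmetic on the SAP's own category limits.

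1. **Where paired readings occur.** Cycle 1 Days 1 and 15 have both readings under Table 1 and under the visit lists. The missing rule therefore matters whichever schedule sites follow. Day 1 of Cycles 2 to 24 adds further pairs only under the visit lists. From Cycle 26, the late-treatment schedule asks for an ECG at each visit with no pair.

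2. **What the missing rule does.** On Cycle 1 Day 1 the predose reading is the baseline (protocol 9.1.4.3.1; SAP 3.1.6 accepts a same-day predose value), so its change is 0. Let the postdose change be d, with 30 < d ≤ 60 msec.
   - Predose reading used: change 0, band up to 0.
   - Average of the two used: d/2, so 15 < d/2 ≤ 30, band above 0 to 30.
   - Postdose or highest reading used: d, band above 30 to 60.

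   One patient at one visit can fall in three different cells, and the SAP does not choose among them. It also does not say, for these tables, how the three replicates at a time point are combined.

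3. **Which ECGs the exclusion removes.** Symptom-triggered ECGs have no place in Table 1 other than the Unscheduled column. The weekly ECGs after a dose reduction are less clear. Footnote h requires them, but they have neither a column nor a visit section. Day 15 chemistry in Cycles 2 to 6 also lacks a column, yet it has its own visit section (12.2.11). The status of the weekly ECGs is therefore unstated, and calling them unscheduled is an inference.

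4. **What the adverse event tables recover.** Under 12.1.9, a change above 60 msec or a value of 500 msec or more requires further monitoring. The same section sends to the adverse event form "Abnormalities in the ECG that lead to a change in patient management (e.g., requirement for additional medication or monitoring", along with abnormalities that produce signs or symptoms. SAP 3.10.1 then counts them: treatment-emergent events are tabulated, and "TEAEs leading to dose modification/discontinuation will be summarized by treatment arm, SOC, and PT". These cases should not be lost.

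5. **What remains.** Take an asymptomatic value above 480 and below 500 msec, with a change of 60 msec or less and no change in management. It needs a baseline above 480 − 60 = 420 msec. Exclusion 20 allows a baseline up to 470 msec, so the case is possible. Found only at an unscheduled ECG, it reaches a summary table only if the investigator records an adverse event. If it persists to the next Day 1, it appears in that visit's row. It also exceeds the 470 msec limit for starting a cycle (9.1.3.1), so continuing needs the Medical Monitor's permission.

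6. **The schedule conflict, in procedures.** Table 1 requires 2 postdose triplicate sets (Cycle 1 Days 1 and 15). The visit lists add one at each Day 1 from Cycle 2. A patient treated to the assumed median PFS of 4.5 months reaches 4.5 × 28 = 126 days, or about 137 days in calendar months. Cycle 5 starts on day 4 × 28 + 1 = 113 and Cycle 6 on day 5 × 28 + 1 = 141, so four visits (Cycles 2 to 5) are in conflict: 2 sets against 2 + 4 = 6. This counts procedures, not missed events.

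**The case against.** The strongest reply is that little is lost. SAP 3.10.4 does give QTc its own summary, as protocol 13.4.6.5 promised, with value bands, change bands and statistics at each time point. Row layout is normally settled in table shells, and SAP section 4 puts the table list in a separate document. The serious values have an adverse event route, and all readings remain in listings, which can be read in full for 40 patients. No text requires a worst post-baseline QTcF table.

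Most of this stands, and it limits the size of the point. It does not remove it. The exclusion of unscheduled visits is a stated rule, so shells that follow the SAP would carry it over. Adverse event counts depend on what investigators record and do not replace a summary of measured QTcF.

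On the schedule, a reader might infer that the two versions compromise QTc monitoring. The documents do not support that. Either version keeps the predose series, the Cycle 1 postdose readings and the QTcF criteria for starting each cycle. The repeated bullet looks like carried-over text, since it also appears at a visit after the last dose. Section 9.1.4.3.1 points sites to Table 1: "Patients will have ECGs performed at times designated by the protocol (refer to Table 1". Section 12.1.9 adds that "instructions for performing ECG assessments will be provided in the ECG manual", and that manual, not among the documents, may settle the matter. What stands is a drafting inconsistency that could produce uneven extra postdose ECGs across sites.

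**Conclusion.** The point holds as a gap in the safety tables. As written, the QTcF category tables can undercount patients whose highest value or largest change occurs at an unscheduled ECG, and they are ambiguous for every visit with paired readings, at least Cycle 1 Days 1 and 15. What can be missing from all summary tables is mainly asymptomatic, intermediate prolongation at unscheduled ECGs that no one records as an adverse event. This rests on SAP 3.10 and 3.10.4 being followed literally and on the separate table list adding nothing. It extends to the weekly ECGs after a dose reduction only if those are treated as unscheduled.

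The number of prolongations affected cannot be estimated: the documents give neither a QTcF distribution nor peak-to-trough data. A reader might take the roughly 20% rate in protocol 5.2 and infer that 0.20 × 40 = 8 patients could be missed. That does not follow. The rate describes how many patients had prolongation, not how many a table would omit. It comes from machine-read ECGs graded under CTCAE v3, mostly in patients with lung cancer, at 300 mg daily or more or 350 mg intermittently.

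No efficacy conclusion is affected.

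**What to change.** **SAP 3.10.4 (main change).** Present the QTcF value and change categories by visit and time point, with predose and postdose in separate rows, and state how triplicates are combined. Add one table of each patient's worst post-baseline QTcF and worst change from baseline, using all post-baseline ECGs including unscheduled ones, as a named exception to SAP 3.10. That table also makes the status of the weekly ECGs after dose reduction immaterial.

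**Protocol (secondary clean-up).** Align the ECG bullets in 12.2.4–12.2.9 with Table 1 footnote h and 12.1.9, so that only the predose ECG is required from Cycle 2. In 12.2.12, ask for a single triplicate ECG.

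**Cost.** One or two extra safety tables and a protocol clarification. No new data are needed. Even if the protocol wording is corrected too late for patients already treated, the SAP change still works, because it uses ECGs already collected.
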